		ARM F3	Moderna COVID-19 Vaccine
		ARM F4	Sanofi-GSK COVID-19 Vaccine

IS = immunosuppressive; MMF = mycophenolate mofetil; MPA = mycophenolic acid

* The Janssen COVID-19 Vaccine treatment arms are currently closed to enrollment.

Figure 3. Participant Flow Diagram for Adult Stage 2

[figure not shown]
[figure not shown]

Figure 4. Study Flow for Adult Stage 2

3.1.2 Pediatric Population

3.1.2.1 Pediatric Stage 1

The pediatric portion of this trial will enroll up to a maximum of 800 participants (2 through 17 years of age) with a Roche Elecsys® Anti-SARS-CoV-2 S result ≤ 2500 U/mL after receiving an age-appropriate EUA-authorized initial COVID-19 vaccine regimen as shown in [Table 6](#) (up to 80 participants per arm). Vaccines will be included in this protocol as they receive EUA or approval by FDA for a given age group. Pediatric participants will have 1 of 4 autoimmune diseases: pediatric SLE, JIA, JDM, or POMS.

Participants will be assigned to 1 of 3 cohorts based on their IS regimens:

- Cohort A: Receipt of MMF or MPA (\pm other rheumatic disease medications, including biologics)
 - Participants who are taking MMF or MPA (without additional B cell depleting medications or MTX) will be placed in this cohort.
- Cohort B: Receipt of MTX (\pm other rheumatic disease medications, including biologics)
 - Participants who are taking MTX (without additional B cell depleting medications or MMF/ MPA) will be placed in this cohort.
- Cohort C: Receipt of BCDT within the past 18 months (\pm other rheumatic disease medications)
 - Participants taking B cell depletion medications, regardless of whether they are also taking MMF or MTX, will be placed in this cohort.

Treatment Arms: Participants in Cohorts A, B, and C will be assigned to receive an additional dose of the same COVID-19 vaccine as their original vaccine series. [Table 6](#) describes the age-appropriate qualifying initial COVID-19 vaccine regimen for participation in Pediatric Stage 1.

Update: Beginning with v6.0 of the protocol, bivalent versions of the mRNA vaccines, Moderna and Pfizer-BioNTech COVID-19 vaccines, replaced original monovalent versions.

Participants in Cohorts A and B will be randomized into 2 IS medication treatment plans as follows:

- Participants continue to take their cohort-defining IS medications without alterations in schedule and dosing.
- Participants withhold their cohort-defining IS medications before and after the additional homologous vaccine dose per protocol instructions (see Section 7.1.1 Protocol-mandated Medications).

All potential treatment arms for the pediatric population are detailed in [Table 7](#). As of the date of Protocol Version 5.0, the Pfizer-BioNTech and Moderna COVID-19 vaccines have been authorized for use in children (ages 6 months through 17 years) in addition to adults.

Schedule of Events: Visits to assess endpoints will occur at Baseline (Week 0), Week 4 ± 1 week, Week 12 ± 2 weeks, Week 24 ± 2 weeks, Week 36 ± 2 weeks, and Week 48 ± 2 weeks. Participant and study flow diagrams are provided in Figure 5 and Figure 6, respectively.

A pediatric participant will be enrolled in the study for a maximum of approximately 13 months.

Table 6. Initial COVID-19 Vaccine Regimens Qualifying Participants for Pediatric Stage 1 and ACV01 Stage 1 Study Doses

Pfizer-BioNTech COVID-19 Vaccine		
Age of Participant	Qualifying Regimen	ACV01 Stage 1 Study Dose
2 years through 4 years	3 doses of 3 mcg	3 mcg bivalent
5 years through 11 years *	2 doses of 10 mcg	10 mcg bivalent
12 years through 17 years **	2 doses of 30 mcg	30 mcg bivalent

* Individuals who turned from 4 years to 5 years of age between any doses in the primary series may also have received one or two doses of 3 mcg as part of the qualifying regimen. Individuals who turned from 4 years to 5 years of age after completion of the primary series may also have received three doses of 3 mcg as the qualifying regimen.

**Individuals who turned from 11 years to 12 years of age between doses in the primary regimen may also have received one or two doses of 10 mcg as part of the qualifying regimen. Individuals who turned from 11 years to 12 years of age after completion of the primary series may also have received two doses of 10 mcg as the qualifying regimen.

Moderna COVID-19 Vaccine		
Age of Participant	Qualifying Regimen	ACV01 Stage 1 Study Dose
2 years through 5 years	2 doses of 25 mcg	25 mcg bivalent
6 years through 11 years *	2 doses of 50 mcg	50 mcg bivalent
12 years through 17 years **	2 doses of 100 mcg	100 mcg bivalent

* Individuals who turned from 5 years to 6 years of age between any doses in the primary series may also have received one or two doses of 25 mcg as part of the qualifying regimen. Individuals who turned from 5 years to 6 years of age after completion of the primary series may also have received two doses of 25 mcg as the qualifying regimen.

**Individuals who turned from 11 years to 12 years of age between doses in the primary regimen may also have received one or two doses of 50 mcg as part of the qualifying regimen. Individuals who turned from 11 years to 12 years of age after completion of the primary series may have received two doses of 50 mcg as the qualifying regimen.

[figure not shown]
Table 7. Treatment Arm Assignments in Pediatric Stage 1

		Additional Homologous Vaccine Dose*	Randomized Treatment Plan
Cohort A: MMF or MPA	ARM A1P	Moderna COVID-19 Vaccine	Continue MMF/MPA
	ARM A2P	Pfizer-BioNTech COVID-19 Vaccine	Continue MMF/MPA
	ARM A4P	Moderna COVID-19 Vaccine	Withhold MMF/MPA
	ARM A5P	Pfizer-BioNTech COVID-19 Vaccine	Withhold MMF/MPA
Cohort B: Methotrexate	ARM B1P	Moderna COVID-19 Vaccine	Continue MTX
	ARM B2P	Pfizer-BioNTech COVID-19 Vaccine	Continue MTX
	ARM B4P	Moderna COVID-19 Vaccine	Withhold MTX
	ARM B5P	Pfizer-BioNTech COVID-19 Vaccine	Withhold MTX
Cohort C: B cell depletion therapy	ARM C1P	Moderna COVID-19 Vaccine	N/A
	ARM C2P	Pfizer-BioNTech COVID-19 Vaccine	N/A

IS = immunosuppressive; MMF = mycophenolate mofetil; MPA = mycophenolic acid

[figure not shown]
*Bivalent vaccines will be administered per Section 6, Investigational Agents

Figure 5. Participant Flow Diagram for Pediatric Stage 1

IS = immunosuppressive medications; JDM = juvenile dermatomyositis; JIA = juvenile idiopathic arthritis; POMS = pediatric-onset multiple sclerosis; MMF = mycophenolate mofetil; MPA = mycophenolic acid; MTX = methotrexate; SLE = systemic lupus erythematosus

Figure 6. Study Flow Diagram for Pediatric Stage 1

IS = immunosuppressive medication

3.1.2.2 Pediatric Stage 2

Stage 2 of this trial will include up to a maximum of 480 pediatric study participants (up to 80 per arm) with a Roche Elecsys® Anti-SARS-CoV-2 S result ≤ 2500 U/mL after previous COVID-19 vaccine administration (an age-appropriate EUA-authorized or FDA-approved initial COVID-19 vaccine regimen plus 1 additional dose of the same vaccine as shown in [Table 8](#)). All participants (2-17 years of age) who previously received doses of the Pfizer-BioNTech COVID-19 Vaccine are eligible to receive an age-appropriate dose of the Moderna COVID-19 Vaccine. Participants 12 through 17 years of age who previously received doses of the Moderna COVID-19 vaccine are eligible to receive an age-appropriate dose of the Pfizer-BioNTech COVID-19 Vaccine.

Participants will be eligible to receive a dose of an alternative COVID-19 vaccine. Participants may have received their previous COVID-19 vaccine as a study participant and then enter into Stage 2 (“rollover participant”), or they may have received their previous COVID-19 vaccine prior to enrollment in the study (“newly recruited participant”).

Participants will be allocated to 1 of 3 cohorts based on their IS regimens:

- Cohort D: Receipt of MMF or MPA (\pm other rheumatic disease medications, including biologics)
 - Participants who are taking MMF or MPA (without additional B cell depleting medications or MTX) will be placed in this cohort.
- Cohort E: Receipt of MTX (\pm other rheumatic disease medications, including biologics)
 - Participants who are taking MTX (without additional B cell depleting medications or MMF/ MPA) will be placed in this cohort.
- Cohort F: Receipt of B cell depletion therapy within the past 18 months (\pm other rheumatic disease medications)
 - Participants taking B cell depletion medications, regardless of whether they are also taking MMF or MTX, will be placed in this cohort.

Treatment Arms: Participants in Cohorts D, E, and F will receive a dose of an alternative COVID-19 vaccine compared to their previous COVID-19 vaccine doses. Participants who previously received age-appropriate doses of a single mRNA vaccine (Moderna COVID-19 Vaccine OR Pfizer-BioNTech COVID-19 Vaccine, as noted above) will receive the other mRNA COVID-19 vaccine. [Table 8](#) describes the age-appropriate qualifying COVID-19 vaccine regimen for participation in Pediatric Stage 2.

Update: Beginning with v6.0 of the protocol, bivalent versions of the mRNA vaccines, Moderna and Pfizer-BioNTech COVID-19 vaccines, replaced original monovalent versions.

Participants in Cohorts D and E will withhold their cohort-defining IS medications before and after the alternative vaccine dose per protocol instructions (see Section 7.1.1 Protocol-mandated Medications).

Participants in Cohort F who are taking MMF, MPA, or MTX in addition to B cell depletion therapies (BCDTs) will withhold these medications before and after the alternative vaccine dose per protocol instruction (see Section 7.1.1 Protocol-mandated Medications).

All potential treatment arms for Pediatric Stage 2 are detailed in [Table 9](#).

Schedule of Events: Visits to assess endpoints will occur at Baseline (Week 0), Week 4 ± 1 week, Week 12 ± 2 weeks, Week 24 ± 2 weeks, Week 36 ± 2 weeks, and Week 48 ± 2 weeks. Participant and study flow diagrams for Stage 2 are provided in Figure 7 and Figure 8, respectively.

A participant who enters Stage 2 after a serologic negative, suboptimal, or low immune response to their Stage 1 vaccine dose may be on study for up to a maximum of 26 months. Rollover participants will discontinue follow-up as part of Stage 1 upon rollover into Stage 2. A participant who is newly recruited to the study for entry into Stage 2 may be on study for up to a maximum of 13 months.

Table 8. Qualifying COVID-19 Vaccine Regimens and Study Doses for Pediatric Stage 2 Participants

Pfizer-BioNTech COVID-19 Vaccine		
Age of Participant	Qualifying Regimen	ACV01 Stage 2 Study Dose of Moderna
2 years through 4 years	4 doses of 3 mcg	25 mcg bivalent
5 years *	4 doses of 3 mcg OR 3 doses of 10 mcg	25 mcg bivalent
6 years through 11 years	3 doses of 10 mcg	50 mcg bivalent
12 years through 17 years **	3 doses of 30 mcg	100 mcg bivalent

* Individuals who turned from 4 years to 5 years of age between any doses in the previous vaccine series may also have received one, two or three doses of 3 mcg as part of the qualifying regimen. Individuals who turned from 4 years to 5 years of age after completion of the previous vaccine series may also have received four doses of 3 mcg as the qualifying regimen.

**Individuals who turned from 11 years to 12 years of age between doses in the primary regimen may also have received one or two doses of 10 mcg as part of the qualifying regimen. Individuals who turned from 11 years to 12 years of age after completion of the primary series may also have received three doses of 10 mcg as the qualifying regimen.

Moderna COVID-19 Vaccine		
Age of Participant	Qualifying Regimen	ACV01 Stage 2 Study Dose of Pfizer-BioNTech
12 years through 17 years *	3 doses of 100 mcg	30 mcg bivalent

**Individuals who turned from 11 years to 12 years of age between doses in their primary vaccine series may also have received one or two doses of 50 mcg as part of the qualifying regimen. Individuals who turned from 11 years to 12 years of age after completion of the previous vaccine series primary series may have also received three doses of 50 mcg as the qualifying regimen.

Table 9. Treatment Arm Assignments in Pediatric Stage 2

	Previous Vaccine Doses	Stage 2 Arm	Stage 2 Alternative Vaccine Dose*
Cohort D: MMF or MPA	Moderna COVID-19 vaccine (from Arms A1P or A4P, or newly recruited) Ages 12-17 only	ARM D1P	Pfizer-BioNTech COVID-19 Vaccine
	Pfizer-BioNTech COVID-19 vaccine (from Arms A2P or A5P, or newly recruited) Ages 2-17	ARM D2P	Moderna COVID-19 Vaccine
Cohort E: Methotrexate	Moderna COVID-19 vaccine (from Arms B1P or B4P, or newly recruited) Ages 12-17 only	ARM E1P	Pfizer-BioNTech COVID-19 Vaccine
	Pfizer-BioNTech COVID-19 vaccine (from Arms B2P or B5P, or newly recruited) Ages 2-17	ARM E2P	Moderna COVID-19 Vaccine
Cohort F: B cell depletion therapy	Moderna COVID-19 vaccine (from Arms C1P, or newly recruited) Ages 12-17 only	ARM F1P	Pfizer-BioNTech COVID-19 Vaccine
	Pfizer-BioNTech COVID-19 vaccine (from Arms C2P or newly recruited) Ages 2-17	ARM F2P	Moderna COVID-19 Vaccine

*Bivalent vaccines will be administered per Section 6, Investigational Agents

Figure 7. Participant Flow Diagram for Pediatric Stage 2

[figure not shown]
[figure not shown]

Figure 8. Study Flow Diagram for Pediatric Stage 2

Pediatric Stage 2: Additional alternative vaccine

3.1.3 Adaptive Design

An adaptive design will be employed in this trial such that cohorts and arms defined by additional vaccine doses and IS treatment plans may be added or modified based on emerging data from existing and new FDA EUA authorizations or approvals of COVID-19 vaccines:

- New cohorts may be defined based on changes in the medication groups if it becomes obvious that certain medications are highly associated with suboptimal or low immune response to initial COVID-19 vaccine regimen.
- Cohorts may limit or expand the autoimmune diseases that are eligible to be included in the clinical trial, and may include expansion cohorts of underrepresented diseases.
- New cohorts may include participants whose antibody response falls to suboptimal or low immune response levels over time.
- Based upon timing of the FDA EUA authorization for children of each of the COVID-19 vaccines used in this trial, the age range of the inclusion criteria may be expanded.
- Allocation or randomization to treatment with new COVID-19 vaccines may be incorporated into the design when the products become available.
- Identification of additional strategies to enhance vaccine responsiveness in autoimmune diseases, including a temporary switch of immunomodulatory medications.

3.2 Primary Endpoint

The primary endpoint in the adult and pediatric populations of a protective antibody response at Week 4 will be assessed by the NIAID-VRC MSD 3 plex (Wu-1 full-length spike, RBD, and N proteins) assay.

3.3 Secondary Endpoints

Secondary endpoints related to antibody response will primarily be assessed by the NIAID-VRC MSD 3 plex (Wu-1 full-length spike, RBD, and N proteins) assay; where applicable, they will also be assessed by the Roche Elecsys® Anti-SARS-CoV-2 S electrochemiluminescence immunoassay.

The secondary endpoints are applicable to both the adult and pediatric populations.

- Seroconversion at Week 4 following additional doses of COVID-19 vaccine in the subgroup of participants that are anti-COVID-19 antibody negative at Week 0.
- Fold increase in anti-COVID-19 antibody levels at Week 4 following an additional dose of COVID-19 vaccine in the subgroup of participants who are anti-COVID-19 antibody positive at Week 0.
- Longitudinal changes in anti-COVID-19 antibody responses from Week 0 to Weeks 4, 12, 24, 36, and 48.
- Longitudinal changes in neutralization and pseudo neutralization assays from Week 0 to Weeks 4, 12, 24, 36, and 48.
- Changes in disease activity after receipt of additional doses of COVID-19 vaccine as measured by the Clinical Global Impression of Change (CGI-C).
- Changes in disease activity after receipt of additional doses of COVID-19 vaccine as measured by the Physician Global Assessment (PGA).
- Changes in disease activity after receipt of additional doses of COVID-19 vaccine as measured by the following disease-specific assessments:
 - Adult population disease assessments:

- Hybrid Systemic Lupus Erythematosus Disease Activity Index (H-SLEDAI) and Thanou modified Safety of Estrogens in Lupus Erythematosus: National Assessment– Systemic Lupus Erythematosus Disease Activity Index (SELENA-SLEDAI) Flare Index for SLE
- Disease Activity Score 28 using C-reactive protein (DAS28-CRP) for RA
- Flare assessment for SSc (including patient reported flare assessment)
- Pemphigus Disease Area Index (PDAI) for pemphigus
- Physician-assessed relapse for MS
- Pediatric population disease assessments:
 - JIA:
 - JADAS10 for polyarthritis, enthesitis related to JIA, oligoarthritis, and psoriatic arthritis
 - Psoriasis Area and Severity Index (PASI) for psoriatic arthritis
 - SLEDAI-2K and Childhood-onset SLE Criteria for Global Flare [1] for pediatric SLE
 - Childhood Myositis Assessment Scale (CMAS) and Flare Assessment for JDM (Disease Activity Score [DAS]) for JDM
 - Physician-assessed relapse for MS for POMS
- Changes in patient-reported outcomes as measured by:
 - Participant-Reported Outcomes Measurement Information System (PROMIS) 29 (adults only)
 - Pediatric Quality of Life Inventory™ (PedsQL) (pediatrics only)
 - Patient Global Assessment (PtGA)
 - Patient Global Impression of Change (PGI-C)
- The proportion of participants who experience the following safety events:
 - Any Grade 1 or higher AEs related to the additional doses of COVID-19 vaccine
 - Any SAEs, MAAEs, NOCMCs
 - Any SARS-CoV-2 infection

3.4 Exploratory Endpoints

The exploratory endpoints are applicable to both the adult and pediatric populations.

- Changes in autoantibody levels after COVID-19 vaccination between Week 0 and Weeks 4, 12, 24, 36, and 48.
- Assessments of cellular and mechanistic response, including
 - Immune cell population profiling over time
 - Antigen-specific T cell responses
 - Antigen-specific memory B cell responses
 - Total IgG responses
 - B cell and T cell repertoire
 - Changes in gene expression profile modules
 - Plasma levels of soluble mediators

3.5 Stratification, Randomization, and Blinding

When employed in any population, randomization will be accomplished through a password-protected, web-based randomization system. The investigators, clinic personnel, and participants will not be blinded to randomized treatment assignments. Statistical and project staff at the Statistical and Clinical Coordinating Center (SACCC) and the DAIT Medical Monitor and Project Manager will be unblinded to individual treatment assignments as well. Laboratories performing assays for this protocol will be blinded to the identity and group assignment of biological materials to be studied.

The same password-protected, web-based system will be used for allocation of participants to arms and associated tasks and tracking when randomization is not employed.

3.5.1 Adult Population

3.5.1.1 Adult Stage 1

Participants who sign the informed consent form and meet all eligibility criteria for Adult Stage 1 will be assigned to cohorts defined by IS medication (Cohort A: MMF/MPA; Cohort B: MTX; and Cohort C: BCDT) and by the initial COVID-19 vaccine regimen received (Moderna COVID-19 Vaccine, Pfizer-BioNTech COVID-19 Vaccine, or Janssen COVID-19 Vaccine). Participants in Cohort C will be allocated to continuing to take their prescribed IS medications throughout the trial. Participants in Cohorts A and B will be randomized in a balanced fashion (1:1), within the cohorts defined by IS medication and initial COVID-19 vaccine regimen, to one of the available IS medication treatment plans (continue cohort-defining IS vs. withhold cohort-defining IS). Randomization will be performed using a permuted block design stratified by disease type.

A total of 60 participants with a Roche Elecsys® Anti-SARS-CoV-2 S result ≤ 200 U/mL will be randomized or allocated to each arm. In each arm, the number of participants with Roche Elecsys® Anti-SARS-CoV-2 S results ≤ 50 U/mL will be capped at 40 participants, and the number of participants with Roche Elecsys® Anti-SARS-CoV-2 S results > 50 U/mL and ≤ 200 U/mL will be capped at 40 participants.

3.5.1.2 Adult Stage 2

Participants who have signed the informed consent form and meet all eligibility criteria for Adult Stage 2 will be allocated to cohorts defined by IS medication (Cohort D: MMF/MPA; Cohort E: MTX; and Cohort F: BCDT) and by the previous COVID-19 vaccine regimen. See Section 3.1.1.2 Adult Stage 2 for treatment arm vaccine assignments.

Participants in Cohort D will withhold their MMF/MPA, participants in Cohort E will withhold their MTX, and any participants in Cohort F (BCDT) who are also taking MMF/MPA or MTX will withhold these medications. No randomization will be employed.

A total of 80 participants with a Roche Elecsys® Anti-SARS-CoV-2 S result ≤ 2500 U/mL will be allocated to each arm. In each arm, the number of participants with Roche Elecsys® Anti-SARS-CoV-2 S results ≤ 200 U/mL will be capped at 40 participants; the number of participants with Roche Elecsys® Anti-SARS-CoV-2 S results > 200 U/mL and ≤ 2500 U/mL will be capped at 40 participants.

3.5.2 Pediatric Population

3.5.2.1 Pediatric Stage 1

Participants and their legal guardian(s) who sign the consent and assent forms, as appropriate to age, and meet all eligibility criteria for Pediatric Stage 1 will be assigned to cohorts defined by IS medication (Cohort A: MMF/MPA; Cohort B: MTX; and Cohort C: BCDT) and by the initial COVID-19 vaccine regimen received. Participants in Cohort C will be allocated to continuing to take their prescribed IS medications throughout the trial. Participants in Cohorts A and B will be randomized in a balanced fashion (1:1), within the cohorts defined by IS medication and initial COVID-19 vaccine regimen, to one of the available IS medication treatment plans (continue IS vs. withhold IS). Randomization will be performed using a permuted block design stratified by disease type.

A total of 80 participants with a Roche Elecsys® Anti-SARS-CoV-2 S result ≤ 2500 U/mL will be randomized or allocated to each arm. In each arm, the number of participants with Roche Elecsys® Anti-SARS-CoV-2 S results ≤ 200 U/mL will be

capped at 40 participants, and the number of participants with Roche Elecsys® Anti-SARS-CoV-2 S results >200 U/mL and ≤ 2500 U/mL will be capped at 40 participants.

3.5.2.1 Pediatric Stage 2

Participants who have signed the informed consent and assent forms, as appropriate to age, and meet all eligibility criteria for Pediatric Stage 2 will be allocated to cohorts defined by IS medication (Cohort D: MMF/MPA; Cohort E: MTX; and Cohort F: B cell depletion therapy) and by the previous COVID-19 vaccine regimen (Pfizer-BioNTech COVID-19 Vaccine in ages 2 through 17 years or Moderna COVID-19 Vaccine in ages 12 through 17 years). Participants in Cohort D will withhold their MMF/MPA, participants in Cohort E will withhold their MTX, and any participants in Cohort F (B cell depletion therapy) who are also taking MMF/MPA or MTX will withhold these medications. No randomization will be employed.

A total of 80 participants with a Roche Elecsys® Anti-SARS-CoV-2 S result ≤ 2500 U/mL will be allocated to each arm. In each arm, the number of participants with Roche Elecsys® Anti-SARS-CoV-2 S results ≤ 200 U/mL will be capped at 40 participants, and the number of participants with Roche Elecsys® Anti-SARS-CoV-2 S results > 200 U/mL and ≤ 2500 U/mL will be capped at 40 participants.

4. Selection of Participants and Clinical Sites

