13.4.2 Primary Analysis of Primary Endpoint

The primary endpoint of a protective antibody response will be the proportion of participants who reach the laboratory-defined threshold for the NIAID-VRC MSD 3 plex (Wu-1 full-length spike, RBD, and N proteins) assay. Participants with missing Week 4 anti-COVID-19 antibody response data with a documented COVID infection will be considered as not having a protective antibody response. All other participants missing Week 4 anti-COVID-19 antibody response data will be considered to be missing-completely-at-random (MCAR). Intercurrent events which result in Week 4 anti-COVID-19 antibody response data being unevaluable for immune response, including receipt of monoclonal antibodies or plasma products directed against SARS-CoV-2 and any SARS-CoV-2 vaccine outside of the study, will also result in data being considered to be missing-completely-at-random (MCAR).

The primary analysis will be evaluated independently within each arm (defined by age, cohort, vaccine, and IS treatment plan) and within subgroups with either a negative or suboptimal response to prior vaccines (defined as Roche Elecsys® Anti-SARS-CoV-2 S result \leq 200 U/mL) or with a low immune response (defined as Roche Elecsys® Anti-SARS-CoV-2 S result $>$ 200 U/mL and \leq 2500 U/mL). The primary analysis will be performed in the vaccinated population. The proportion of participants meeting a protective antibody response criteria will be reported in each arm and subgroup with 90% Clopper-Pearson confidence intervals and analyzed using a one-sided exact test with alpha = 0.05 against the null hypothesis that the probability of achieving a protective immune response is \leq 0.25. P-values will not be adjusted for

multiple comparisons. The primary analysis will also be conducted in the subgroup of participants with a Roche Elecsys® Anti-SARS-CoV-2 S result ≤ 50 U/mL at the Screening visit. Each analysis will occur after the evaluable participants assigned to that arm have completed the Week 4 study visit or are withdrawn from the study.

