In order to account for up to 20% dropout within a given arm of participants missing Week 4 anti-COVID-19 antibody response data without a documented COVID infection, 40 participants within each subgroup defined by the Roche Elecsys® Anti-SARS-CoV-2 S assay. In each arm, the number of participants with Roche Elecsys® Anti-SARS-CoV-2 S results ≤ 200 U/mL will be capped at 40 participants, and the number of participants with Roche Elecsys® Anti-SARS-CoV-2 S results > 200 U/mL and ≤ 2500 U/mL will be capped at 40 participants.

An adaptive design will be employed such that cohorts may be added or modified in light of emerging evidence on autoimmune disease vaccination or of the development and authorization of COVID-19 vaccines.

14. Identification and Access to Source Data

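### Pediatric Stage 1, Cohorts A and B: continue v withhold is randomised without stratifying by Elecsys stratum, although the caps and the primary test are set by that stratum

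*Protocol*

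**What the plan says.** Protocol 3.5.2 (Pediatric Stage 1) has Cohorts A and B "randomized in a balanced fashion (1:1), within the cohorts defined by IS medication and initial COVID-19 vaccine regimen", to continue or to withhold. The stratification follows: "Randomization will be performed using a permuted block design stratified by disease type". No other factor is named, and Protocol 13.3 repeats this. Cohort C is allocated, not randomised.

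The arm target is set in the same section: "A total of 80 participants with a Roche Elecsys® Anti-SARS-CoV-2 S result ≤ 2500 U/mL will be randomized or allocated to each arm". Protocol 13.7 limits the lower stratum in each arm: "results ≤ 200 U/mL will be capped at 40 participants". The same limit applies to >200 to ≤2500 U/mL. The two caps sum to exactly 80, so there is no slack. In Adult Stage 1 (3.5.1) the two caps of 40 exceed the arm total of 60.

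Protocol 13.4.2 sets the level of testing: "The primary analysis will be evaluated independently within each arm (defined by age, cohort, vaccine, and IS treatment plan) and within subgroups" defined by the 200 U/mL cut. The supportive regression in 13.4.3, reused for continue v withhold in 13.4.4, carries disease type and initial immune response coded as antibody negative or positive.

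Neither document says what happens when one arm of a pair reaches 40 in a stratum before the other. The SAP cannot fill the gap: its Sections 3 and 7.2.3 still describe protocol version 3.0, with 60 per arm and a 50/200 U/mL split.

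**The concern.** The design uses the Elecsys stratum to limit enrolment, to size the cells and to define the primary tests, but not to randomise. Two things follow.

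First, the split at 200 U/mL is neither balanced by design nor adjusted for when the plans are compared. Under the negative/positive coding, a child at 100 U/mL and one at 2000 U/mL are both positive. Protocol 1.1 gives reason to think baseline antibody matters: in a cited transplant series, titres rose after a third dose in one third of antibody-negative patients and in all low-positive ones.

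Second, the two arms of a pair do not fill a stratum together. Under a hard per-arm cap, once one arm has 40, either the next child in that stratum can go only to the open arm, at sites that are not blinded (3.5), or the stratum closes and the paired arm stays short.

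Protocol Section 9 calls the effect of withholding a critical part of the study. With Adult Stage 1 closed and Stage 2 not randomised, this is the only randomised comparison still enrolling.

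**Working it through.** **1. The plan's own figure.** Inputs from Protocol 13.7: null rate 0.25, alternative 0.50, one-sided exact test at 0.05, 33 evaluable. The smallest r with P(X ≥ r | 33, 0.25) ≤ 0.05 is 13 (exact size 0.0484). Power is P(X ≥ 13 | 33, 0.50) = 91.9%, so the stated 90% reproduces.

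**2. A full cell after the planned loss.** 40 × 0.8 = 32 evaluable; reject at 13 or more; power 89.2%. This, not 90%, is the fair comparator for a short cell.

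**3. How far apart the paired arms are when one reaches 40.** One pair was simulated with 1:1 permuted blocks in four disease strata. The documents do not give block size, disease mix or titre split. Assumed: blocks of 2 to 6, several disease mixes, and 30% to 70% of children at ≤200 U/mL, with titre either independent of disease or tied to it.

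| Scheme | Mean gap in paired arm | 95th percentile | Chance that fewer than 33 are enrolled |
|---|---|---|---|
| As written, both strata capped | 4.6 to 5.6 | 10 to 13 | 16% to 28% |
| As written, ≤200 stratum, other stratum left uncapped | 4.4 to 6.2 | 10 to 14 | 15% to 34% |
| Blocks by disease × Elecsys stratum | about 2 | 3 to 5 | about 0 |
| The same, with the cap on the pair (80) | under 1 | 2 | about 0 |

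The gap is also the number of assignments, out of 80 per pair and stratum, that could go only to the open arm if the stratum stayed open.

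**4. Power if the stratum closes instead.** A gap of 5 leaves 35 enrolled and 35 × 0.8 = 28 evaluable; reject at 12 or more; power 82.8%. A gap of 12 leaves 28 enrolled and about 22 evaluable; power 73.8%. Averaged over the simulated gaps, with 20% loss, power in the short cell is 0.81 to 0.82 as written and about 0.84 with titre-stratified blocks. Exact power is saw-toothed (30 evaluable gives 81.9%, 28 gives 82.8%), so small differences in count should not be over-read.

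**5. Chance imbalance before any cap is reached.** If half the children are at ≤200 U/mL, the between-arm difference in that share has standard deviation about √(2 × 0.5 × 0.5 / m) with m per arm. For m = 20 this is 0.158; for m = 40 it is 0.112. A 10-point difference is then within one standard deviation. If both arms are filled to 40 and 40, the counts are equal again, so this matters most when accrual stops short of the caps.

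**The case against.** The strongest reply is that little of this reaches the primary analysis. That analysis is a within-arm exact test against 0.25, so knowing the next assignment cannot bias it. This stands. A reader might infer that predictable allocation undermines the primary result; the documents do not support that. Continue v withhold is a secondary contrast, and SAP 8.1.4 treats all secondary analyses as exploratory.

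A reader might also infer that one arm will fill first. That depends on accrual: 800 is a ceiling over ten arms, and nothing in the documents shows a cell reaching 40. Predictability further assumes that sites can see cap status, which 3.5 does not say.

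A third tempting reading is that randomisation takes power from 90% to 83%. That mixes in dropout: the drop from a full cell is 89.2% to 82.8%, in one arm of the pair.

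Enrolment history also softens the gap. Before version 6.0, pediatric entry required ≤200 U/mL, so disease blocks balanced that stratum directly. If 40 per pair had enrolled by then, the mean gap at ≤200 U/mL falls to 3.3 to 4.5; with 60, to 2.5 to 3.4. The actual count is not given, and this does nothing for the upper stratum.

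Chance imbalance under randomisation is not bias, and the negative/positive covariate removes part of it. It does not capture the 200 U/mL split. Cap handling may be set out in a randomisation plan that was not available; if so, the protocol should still state the rule.

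**Conclusion.** The mismatch is real and its size is modest. Titre can be imbalanced by chance between continue and withhold, with only a partial adjustment planned. If, and only if, accrual reaches a cap, about 4 to 6 of 80 assignments per pair and stratum (10 to 14 at the 95th percentile) are either forced into the open arm or lost from the paired arm. A typical loss means 82.8% power instead of 89.2%.

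These gap figures rest on the assumed block size, disease mix and titre split, and on no enrolment before version 6.0. Titre-stratified blocks raise average power in the short cell by only 2 to 3 points. The better reasons to change are balance on a variable the plan already uses for testing, removal of forced assignments, and a much smaller risk of a badly under-filled cell. The point covers Cohorts A and B of Pediatric Stage 1 only. It is a worthwhile, inexpensive improvement, not a flaw in the primary test.

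**What to change.** For new randomisations in Pediatric Stage 1, Cohorts A and B:

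1. Add Elecsys stratum (≤200 v >200 to ≤2500 U/mL) to the permuted-block stratification. The result is available from Screening, before randomisation.
2. Apply the cap to the pair of arms, 80 per stratum in each cohort-by-vaccine cell, and state that a stratum closes in both arms together. Stratification alone still leaves a gap of about 2 from incomplete blocks. Say also how participants who are randomised but not vaccinated count, since Protocol 11.3 excludes them from accrual and makes them up with new ones.
3. Include the Elecsys stratum, or log baseline titre, in the continue v withhold model, and carry this into the SAP when it is updated from protocol version 3.0.

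The cost is reconfiguring the web-based randomisation system. Strata per cell rise from 4 to 8, which adds a few incomplete blocks, and arm counts may differ from 40 by one or two.
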